- 1. The main objective of this 16-week research study is to determine whether a drug called memantine hydrochloride (memantine) has the potential to help improve episodic memory in adolescents and young adults with Down syndrome. Memantine (Namenda®) is a drug approved by the Food and Drug Administration (FDA) for patients with moderate to severe Alzheimer-type dementia. Two hundred persons of both genders with Down syndrome aged 15-32 years will take part in this study. This is a randomized and double blind study. This means that subjects will have a 50/50 chance of being assigned to receive either the memantine capsules or placebo (inactive capsules). Neither the study participants nor the research personnel will know who is receiving active medication or placebo. Based on memantine's mode of action, current knowledge on brain pathology in persons with Down syndrome, and data from a previous pilot clinical trial, we hypothesize that memantine may improve test scores on a test known as the California Verbal Learning Test-II (CVLT-II) short form in young adults with Down Syndrome. This is a highly used and validated test of episodic memory (which is the collection of past personal experiences occurring at a particular time and place that can be explicitly stated verbally). In addition, we will also investigate the effect of memantine on the performance of the participants in other types of cognitive tests, and continue to investigate the safety and tolerability of memantine in adolescents and young adults with Down syndrome. Accordingly, this research project has four specific aims: 1) investigate whether memantine has the potential to improve test scores on the CVLT-II short form in adolescents and young adults with Down syndrome; 2) investigate whether memantine has the potential to improve test scores of the study participants in other cognitive assessments; 3) determine the usefulness of electrophysiological and neuroimaging methods as potential surrogate efficacy measures; and 4) confirm whether memantine is well tolerated by study participants with Down syndrome.
- 2. We hypothesize that memantine may improve episodic memory in adolescents and young adults with Down syndrome, as assessed by the California Verbal Learning Test-II (CVLT-II) short form.

Background

HRP-503BIO	TEMPLATE: Biomedical Protocol		
Approved:	05/11/2018	Prior Version:	1/23/2018

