 - 1.2. Typical Neuropsychological Profile of Individuals with Down syndrome. The best data available report the mean intellectual quotient (IQ) of school age children with Down syndrome to be in the low to mid 40s (Carr, 1988, Pueschel and Hopmann, 1993, Turner and Alborz, 2003). Individuals with Down syndrome display clear deficits in expressive language, syntactic/morphosyntactic processing, verbal working memory, and digit span (Jarrold et al., 2000; Abbeduto et al., 2001; Vicari et al., 2002, 2004; Brock et al., 2005). Until a decade ago, however, the neuropsychological profile of individuals with Down syndrome was thought to faithfully reflect much of the individual's overall level of intellectual disability. The work by Pennington et al. (2003) has considerably changed this picture. These authors used a comprehensive battery of 18 neuropsychological measures and reported that persons with Down syndrome display disproportional weakness in hippocampus-dependent function, even when their level of intellectual disability is taken into account. The hippocampus-dependent measures (all of which required long-term memory) used by these authors were the List Learning from A Developmental Neuropsychological Assessment (NEPSY), the virtual Morris water maze, the Pattern Recognition and Paired Associates Learning (both parts of the Cambridge Neuropsychological Test Automated Battery; or CANTAB), and the Ecological Memory Questionnaire. Findings from parallel benchmark assessments included measures such as digit span, which is another task in which people with Down syndrome historically

HRP-503BIO	TEMPLATE: Biomedical Protocol		
Approved:	05/11/2018	Prior Version:	1/23/2018

have performed disproportionally poorly (Seung and Chapman, 2000; Brock and Jarrold, 2005), and were in general agreement with the historical Down syndrome literature.

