The chemical name for memantine hydrochloride (see structural formula in Figure 1) is 1-amino-3,5-dimethyladamantane hydrochloride. (The molecular formula for memantine hydrochloride is C12H21N·HCl and the molecular weight is 215.76.) Memantine is an uncompetitive, moderate affinity, antagonist of NMDA receptors. It has been proposed that therapeutic doses of this drug inhibit the pathologic effect of NMDA receptor activation while leaving unaffected NMDA receptor-mediated physiological processes involved in learning and memory. After oral administration, memantine is quickly and completely absorbed through the gastrointestinal tract with bioavailability close to 100%. Food has no impact on the rate of absorption and the time to reach peak serum concentration is 3–8 hours, and its half-life is 60–80 hours (Kornhuber et al., 2007; Parsons et al., 2007). Over 80% of the drug is excreted via the kidneys unchanged in the urine and in patients with severe renal impairment the dose should be limited to 5 mg twice daily. Minimal metabolism occurs in the liver and there is little involvement of hepatic microsomal p450 iso-enzymes, except for selective inhibition of cytochrome CYP2B6, with minimal drug-drug interactions (Kornhuber et al., 2007). In all clinical trials, memantine was found safe and well tolerated, with a favorable profile of adverse effects. These have been described as mild to moderate and comparable to placebo. The

most frequently observed adverse effects in adult trials are dizziness, constipation, headache, hypertension and somnolence (Sani et al., 2012). The tolerability of an NMDAR antagonist depends upon its affinity toward the receptors, unbinding kinetics, and voltage dependency. Memantine is thought to improve the fidelity of glutamatergic synaptic transmission by voltage-dependently binding to the to the NMDA receptor at or near the Mg2+ binding site with an affinity larger than Mg2+ itself. Such action is predicted to provide both neuroprotection and symptomatic restoration of synaptic plasticity by one and the same mechanism (Parsons et al., 2007; Danysz and Parsons, 2012).

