memantine or placebo on cognitive and adaptive functions of 40 young adults (aged 18-32 years) with Down syndrome, using a broad and carefully selected set of neuropsychological outcome measures. The primary measures of this study were the Paired Associate Learning (PAL) and Pattern Recognition Memory (PRM) tests. We also included two additional secondary measures associated with the primary hypothesis that memantine therapy would produce improvements in test scores on hippocampusdependent measures. These additional measures were the short form of the California Verbal Learning Test-II (CVLT-II) and the Rivermead Behavioral Memory Test-Children's version (RBMT). Safety and tolerability were also monitored. This was the first clinical study in Down syndrome to benefit fully from the lessons learned from preclinical work in animal models and recent neuropsychological findings in persons with Down syndrome. Although no significant differences were observed between the memantine and placebo groups on the two primary outcome measures, we found a significant effect of memantine therapy on the CVLT-II short form. The CVLT-II measures supraspan word learning ability (i.e., word lists with number of words larger than the typical 7±2 span of short term memory) as an index of episodic verbal long-term memory, and is known to be sensitive to posterior hippocampal functioning (based on neuroimaging) and to be impaired in patients with various forms of degeneration or damage to the hippocampus. Additionally, the study showed a P-value <0.10 for one of the primary outcome measures: the number of stages completed in the PAL. This is a measure of non-verbal memory that requires the participant to learn associations between an abstract visual pattern and its location. A P-value < 0.10 was also detected for one of the secondary outcome measures, the Recall of Digits test (which is part of the Differential Ability Scales; DAS-II). This is a measure of rote short-term verbal memory in which the participant is asked to repeat, in the same order, an increasingly longer string of single digit numbers verbally presented by the examiner. Memantine was well tolerated, with only infrequent and mild adverse events noted (two participants in the memantine arm showed increased anxiety and one displayed echolalia, as reported to the investigators by their caregivers). With only 37 participants (out of 40 recruited and randomized) completing the study, the small sample size was the obvious limitation of this study.

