Safety and tolerability will be monitored primarily by physical examinations, electrocardiograms (ECGs), comprehensive clinical laboratory tests, incidence of adverse event recording, and the Screen for Childhood Anxiety Related Emotional Disorders (SCARED), which is a subject and parent self-report instrument used to screen for childhood anxiety disorders including general anxiety disorder, separation anxiety disorder, panic disorder, and social phobia. In addition, it assesses symptoms related to school phobias. The comprehensive clinical laboratory tests will include assessments of liver and kidney function, electrolytes, acid/base balance, and blood glucose and proteins (see Section 7.2., Laboratory Determinations, for a complete description of the laboratory tests to be used). This clinical trial will involve 2 comprehensive clinical laboratory tests per subject (baseline and 16th treatment week). ECGs, with interpretation by the Cardiology Service, and will involve 2, 12-lead, ECGs per subject. Clinical consultations will be performed either by a board certified developmental pediatrician ([name]) or two board certified psychiatrist ([name] and [name]), or medical residents or fellows under their supervision.

The physical exam will include a health questionnaire addressing the study exclusion criteria. In a checklist format, aspects of the general and neurological exam are to be documented with attention to such aspects as balance, extra ocular movements, optokinetic nystagmus (OKN), tremor, and other movement disorders (see neurological examination checklist).

- 2. Provide a description of all study-related research procedures being performed including procedures being performed to monitor research participants for safety or minimize risks.
 - Visit 1: Baseline physical examination and laboratory tests will be performed by a board certified physician in this visit. Subjects will receive a physical examination, vital signs will be measured, and an electrocardiogram (ECG) will be performed. The subject's medical records also will be reviewed. At the end of the visit, blood samples will be collected for a comprehensive battery of clinical laboratory tests. Below is the list of general procedures to be followed in this visit:
 - Vital Signs
 - Clinical History Taking
 - Complete Physical Exam
 - Neurological Exam
 - The Screen for Childhood Anxiety Related Emotional Disorders (SCARED)
 - Concomitant Medication Check
 - 12-lead ECG

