In addition to the scheduled measurements, inquiries will be made at each evaluation period as to the presence of any adverse experiences by asking general questions such as, "How are you feeling? Have you had any problems since the last visit? Have you been sick or gone to the doctor? Are you taking any new medicines?" Should information on adverse experiences be elicited during this questioning, the information will be recorded in the CRF.

In addition to expert medical evaluations during the medical visits (Visits 1, 3, and 5), periodic review of adverse events in this trial will be performed. The function of the DSMB is to monitor the safety data being generated by the clinicians in this trial to determine if the risk/benefit ratio is acceptable to continue this trial. [name] will participate in the open portion of meetings to be appraised of the group decisions and any suggestions to improve the safety and reliability of trial procedures (made during their closed deliberations), but he will not have any say in terms of the appropriateness of the continuation of the trial. The formal charter of the DSMB will be prepared and approved at the DSMB organizational meeting. Written reports will be generated annually, in case no serious adverse event (SAE) is reported. In addition to its annual meeting, the board may also meet within 48 hours of the occurrence of a severe adverse event (SAE) to plot an appropriate course of action for the remainder of the trial, and should generate a detailed report of their decision within one week from the time a SAE has been noted and properly reported. DSMB meetings may occur more often than annually at the discretion of the DSMB Chairperson.

HRP-503BIO	TEMPLATE: Biomedical Protocol					
Approved:	05/11/2018	Prior Version:	1/23/2018			

In case of a serious adverse event (SAE), the subject will be dropped immediately from the study, and the investigators will notify the Institutional Review Board (IRB) within 24 hours and file a form 3500A – Medwatch SAE form with the FDA. (Form 3500A – Medwatch is appended to the Case Report Form - CRF) (see APPENDIX 4).

SAE monitoring and reporting for the São Paulo site will follow the same general standard operating procedures. In addition, the São Paulo site will have to comply with Brazilian federal, state, and local rules and regulations for the performance of clinical trials.

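### Dizziness, headache, constipation, somnolence and echolalia are sought only through general questions at weeks 8 and 16, with no pre-dose baseline, which pulls the tolerability comparison toward no difference

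*Combined protocol and SAP*

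**What the plan says.** The fourth specific aim is to "confirm whether memantine is well tolerated by study participants with Down syndrome".

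Background section 1.3 reports that the "most frequently observed adverse effects in adult trials are dizziness, constipation, headache, hypertension and somnolence". Section 1.5 adds what the pilot saw in this population: "two participants in the memantine arm showed increased anxiety and one displayed echolalia, as reported to the investigators by their caregivers". The section on risks to participants gives these as 2 of 18 (11.1%) and 1 of 18 (5.6%).

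Safety monitoring is broader than symptom enquiry: "Safety and tolerability will be monitored primarily by physical examinations, electrocardiograms (ECGs), comprehensive clinical laboratory tests, incidence of adverse event recording", together with the SCARED anxiety questionnaire. For symptoms, item 3 of Study Design, Procedures and Timeline says: "inquiries will be made at each evaluation period as to the presence of any adverse experiences by asking general questions". The examples that follow ask how the participant is feeling, whether there have been problems since the last visit, whether a doctor was seen, and whether there are new medicines. Table 1 marks adverse event monitoring at Visits 3 and 5 only.

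On the population, section 1.2 says: "Individuals with Down syndrome display clear deficits in expressive language". The paragraph on duration of testing gives pilot mean mental ages of 6.1 years (placebo) and 7.6 years (memantine).

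**The concern.** Dizziness, headache, somnolence and constipation are mostly felt rather than seen, and are often reported only when someone asks about them by name. The questions given as examples are open, addressed to the participant, and rely on that person to volunteer the symptom. The first scheduled enquiry is at week 8, while the stated titration runs over weeks one to four. A short-lived early symptom would therefore have to be recalled unprompted weeks later.

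Without a symptom record before dosing, a complaint present all along cannot be told apart from a new or worsened one.

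The trial wants to be able to say that memantine is well tolerated. If symptoms are missed equally in both blinded arms, the observed difference is too small, and the error favours that conclusion.

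**Working it through.** **Step 1. Which named effects have a targeted measure in the visible text?**

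| Effect | Where named | Targeted measure described |
|---|---|---|
| Hypertension | 1.3 | Yes: blood pressure at Visits 1, 3 and 5 |
| Anxiety | 1.5, Risks | Yes: SCARED at Visits 1 and 5 |
| Dizziness | 1.3 | In part: balance on the neurological checklist; the symptom itself is not asked about |
| Headache | 1.3 | None |
| Constipation | 1.3 | None |
| Somnolence | 1.3 | None directly; SIB-R includes withdrawn or inattentive behaviour |
| Echolalia | 1.5, Risks | None directly; SIB-R includes unusual or repetitive habits |

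Four of the five adult-trial effects, plus echolalia, therefore depend on the general enquiry and on what the caregiver volunteers. Medical history is taken at screening and Visit 1, but no pre-dose symptom record in the same form as the on-treatment enquiry is described.

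**Step 2. Pilot rates.** 2/18 = 11.1% and 1/18 = 5.6%, as the protocol states. These are the only adverse event rates given for this population, and no placebo rate accompanies them.

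**Step 3. Direction.** Let p1 and p0 be the true risks on memantine and placebo, and s the fraction of events captured. Blinding makes the same s in both arms a reasonable assumption. Then

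expected observed difference = s·p1 − s·p0 = s(p1 − p0).

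For any s below 1 the absolute difference moves toward zero. The risk ratio keeps its expected value, but it is estimated from fewer events.

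**Step 4. Why no size can be given.** The documents state no s, no placebo rate and no planned test for adverse events. The figures below are illustrations: 100 per arm, pooled two-proportion z test, one-sided 0.025 (z > 1.96), exact binomial enumeration.

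| Assumed true risks | Excess | Power at s = 1 | s = 0.5 | s = 0.25 |
|---|---|---|---|---|
| 12% v 3% | 4-fold | 71% | 37% | 18% |
| 15% v 5% | 3-fold | 68% | 35% | 18% |
| 10% v 5.5% | 1.8-fold | 22% | 11% | 7% |
| 5% v 3% | 1.7-fold | 9% | 6% | 2% |

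The first two rows show a large loss, but they assume three- to fourfold excesses. The section on risks says that in controlled dementia trials no event reached both 5% frequency and twice the placebo rate. Under excesses below twofold, power is low even with full capture, so the sample size limits detection before the question wording does.

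**Step 5. Would nothing be seen?** No. At a true 12% and s = 0.25, the captured risk is 3%, and the chance of at least one recorded event among 100 memantine participants is 1 − 0.97^100 = 95%.

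**The case against.** The strongest reply is that the open questions are one layer among several. The protocol says so: "In addition to the scheduled measurements, inquiries will be made at each evaluation period". Examinations, ECG, laboratory tests and SCARED are scheduled. The protocol also designates PPVT-IV, TROG and SIB-R as secondary tolerability measures for subtle events that a physician might miss. Inclusion criterion 12 requires the same caregiver, in daily contact, to attend and give information. Commitment to report adverse events is checked at consent, and all three pilot events came from caregivers. Telephone prescreening asks whether the person communicates verbally, and the trial targets a mental age of at least 5 years. The listed questions are examples, and the case report form is a separate appendix that may already contain a symptom list.

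Much of this stands. A reader might infer that adverse events are sought only through open questions; the passages just listed contradict that. A reader might also infer that the protocol expects the five effects in this trial. Section 1.3 only reports adult trials and describes effects there as comparable to placebo.

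What the reply does not remove is the gap in Step 1. ECG and laboratory tests do not detect headache or somnolence. A fall in a test score does not identify its cause. The caregiver is a real channel, but the visible text gives that person no question on these symptoms. The protocol accepts the principle elsewhere: it added SCARED because caregivers had reported anxiety in the pilot. No comparable item is described for echolalia, reported through the same channel.

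**Conclusion.** The point holds in a limited form. For dizziness, headache, constipation, somnolence and echolalia, the only elicitation described is general enquiry at weeks 8 and 16, without a pre-dose symptom baseline. Under-recording in both arms is likely and would move the arm comparison toward no difference. This rests on two assumptions: that open questions miss some of these symptoms in people with limited expressive language, and that they miss them about equally in the two blinded arms.

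The size cannot be found from the documents. Three stronger readings are not supported:

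- That the tolerability aim will find nothing. Step 5 shows events would still be recorded.
- That power falls from about 70% to below 20%. Those figures need assumed capture fractions and excesses larger than the comparative evidence the protocol cites, although that evidence comes from elderly patients with dementia.
- That the pilot summary's silence on the five effects among 18 memantine participants shows under-recording. At a combined incidence of 5% to 10%, zero of 18 has probability 0.95^18 = 40% to 0.90^18 = 15%, and the full pilot report is an appendix not seen here.

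This is a worthwhile, inexpensive improvement and does not threaten the trial's validity.

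**What to change.** In item 3 of Study Design, Procedures and Timeline, keep the open questions, asked first. If the case report form already holds a symptom list, refer to it there. Otherwise add a short fixed yes/no list: dizziness, headache, somnolence, constipation and echolalia. Anxiety stays with SCARED.

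Ask both caregiver and participant, in the same words at both sites, once before dosing (Visit 1 or 2), at Visits 3 and 5, and at the Treatment Discontinuation Visit. Mark it in Table 1.

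In the Data Analysis Plan, which specifies no between-arm adverse event analysis, state that each item will be reported as new or worse since baseline, by arm, with the risk difference and its 95% confidence interval.

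The cost is one case report form page in English and Portuguese and a few minutes at visits already scheduled. The downside is more minor events recorded in both arms; the pre-dose list and the placebo arm allow for that.

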At the end of this visit, a prescription will be submitted to the Investigational Drug Services (IDS) at University Hospitals in the Cleveland site where a study coordinator will dispense a 60-day supply (56 days plus 4 extra days) of either memantine capsules or identically-looking placebo capsules and repeat to the parent/guardian/next-of-kin caretaker the necessary information on the use of the medication. For the 16-week duration of this study, capsules will be taken either once (first week) or twice daily by mouth according to memantine's standard titration schedule. In the São Paulo site, a physician at the Hospital Israelita Albert Einstein (English: Albert Einstein Israelite Hospital) will provide a 60-day supply of either memantine capsules or identically-looking placebo capsules, which will come randomized and prepackaged from the University of Iowa Pharmaceuticals Services.

For a subset of 30-60 participants in the Cleveland site, magnetic resonance imaging (MRI) of the brain will be performed at the Cleveland Clinic in the afternoon, one or two hours after the completion of the neuropsychological test battery. (Note that consent to participate in this particular subset of the study is independent from the overall consent to participate in the study, therefore, the final number of participants here will depend on the number of participants who agree on participating in the clinical trial AND on this component of the study.)

Visit 3: First follow-up medical visit at 8 weeks from the start of the medication. This visit is to ensure that the study medication is being adequately tolerated. The same clinical procedures will be followed as were done during Visit 1. Vital signs will be measured and a physical examination will be performed. At this visit, a final, 60-day, supply of study medication will be dispensed. The general procedures to be followed in this visit are listed below:

HRP-503BIO	TEMPLATE: Biom	edical Protocol	
Approved:	05/11/2018	Prior Version:	1/23/2018

- Vital Signs
- Adverse Event Assessment
- Medication Compliance Check
- Complete Physical Exam
- Neurological Exam
- Concomitant Medication Check
- Urine pregnancy test for females of childbearing potential
- Dispensing of Medication

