Approved:	05/11/2018	Prior Version:	1/23/2018

A fast of at least 2 hours from food and beverages except water is required prior to collection of blood samples. All clinical laboratory testing in Cleveland will be conducted by the University Hospitals' central clinical laboratory facility, and by a single accredited clinical laboratory to be contracted by [name] in São Paulo.

Hematology: red blood cell count, hemoglobin, hematocrit, indices, white blood cell count (with differential), and platelet count.

Clinical Chemistry: sodium, potassium, chloride, glucose, urea nitrogen, creatinine, calcium, total bilirubin, total protein, albumin, aspartate aminotransferase, alanine aminotransferase, alkaline phosphatase, and lactate dehydrogenase.

Thyroid Function: total T4, free T4, and TSH at screening; and TSH after treatment.

Routine Urinalysis: pH, protein, glucose, ketones, hemoglobin or blood, specific gravity, and microscopic examination of the sediment.

Additional Labs: β -HCG (females) and serum Hemoglobin A1c (HbA1c) for all subjects with diabetes (at screening only).

12-Lead Electrocardiogram

The electrocardiogram (ECG) will be a complete, standard 12-lead recording. A copy of the ECG and the evaluation report by the Department of Cardiology at University Hospitals or a Board Certified Cardiologist in São Paulo will be kept in the investigator's subject file and appended to the Case Report Form (CRF)(see Appendix 3).

Karyotype

If results of previous karyotyping are not available this must be performed at the baseline visit (Visit 1). A copy of the results, whether conducted prior to baseline visit or at the baseline visit, must be appended to the subjects CRF and the appropriate page of the CRF completed. If this has been done previously, all efforts should be made to obtain the medical records.

At the end of Visit 2 ("Baseline neuropsychological assessments"), subjects will receive either memantine or placebo. Assignment to a treatment group will be according to a computer-generated randomization schedule. The drug dosage will follow memantine's standard titration schedule (i.e., 5 mg/d week one, 5 mg/BID week two, 5 & 10 mg/d divided dose week three, 10mg/BID week four).

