In line with the relatively long half-life of the compound, the safety databases from the FDA and European Union do not list any signs or symptoms of withdrawal after discontinuation of memantine treatment; however, this issue has not been systematically evaluated. In addition, no cases of memantine abuse have been reported to date. However, the caregivers for all participants will be instructed in the consent form that the participants need to be referred to their primary care provider in the unlikely event of behavioral deterioration following discontinuation of memantine treatment in this study.

Describe when research procedures will take place and the duration of an individual subject's participation in the study. Use of the descriptive table listing the study procedures that indicates the visit/week of the interventions below is encouraged.

TABLE 1	SCREENIN G VISIT	VISIT 1	VISIT 2	VISIT 3	VISIT 4	VISIT 5
	Informal Interview, Informed Consent, EEG	Baseline Medical and Formal Screening	Baseline Neuropsych ological Evaluation, MRI	Week 8, Follow-up Medical Evaluation	Week 16, Final Neuropsych ological Evaluation, MRI	Week 16, Final Medical Evaluation
Explanation of Trial Procedures	Х					
Informed Consent/Assent	Х					
Medical History	Х	Х				
Electrophysiological Assessments	Х					X
Karyotyping	X (obtain copy of results if available)	X (collect blood if necessary)				
Physical Exam	,	X		Х		Х
Vital Signs		Х		Х		Х
Clinical Lab Tests		Х				X X
Screen for Childhood Anxiety Related Emotional Disorders (SCARED)		Х				Х
Pregnancy Test		X (blood)		X (urine)		X (urine)
ECG		Х				Х
Concomitant Meds	Х	Х		X		X
Adverse Events Monitoring				Х		Х
California Verbal Learning Test – CVLT II Short Form		_	X (AM)		X (AM)	
Spatial Span (CANTAB)			X (AM)		X (AM)	
Pattern Recognition Memory – PRM (CANTAB)			X (AM)		X (AM)	

HRP-503BIO	TEMPLATE: Biomedical Protocol		
Approved:	05/11/2018	Prior Version:	1/23/2018

Test of Receptive Grammar 2 – TROG-2	X (AM)	X (AM)
Par Associates Learning – PAL (CANTAB)	X (AM)	X (AM)
Recall of Digits (DAS-II)	X (AM)	X (AM)
Spatial working memory (CANTAB)	X (AM)	X (AM)
Matrices subtest of the (DAS-II)	X (AM)	X (AM)
Go-No Go task	X (AM)	X (AM)
Receptive vocabulary (PPVT-IV)	X (AM)	X (AM)
SIB-R	X (AM)	X (AM)
MRI Neuroimaging of a selected group of 30-60 participants	X (PM)	X (PM)
Medication Compliance Check	X	X

Ra

Radiation and Radioactive Substances	
1. Does the research involve the use of radiation or radioactive substances?	

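### No adverse-event enquiry is scheduled between first dose and week 8, so the whole titration period rests on recall and unprompted caregiver reports

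*Combined protocol and SAP*

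**What the plan says.** Tolerability is the fourth specific aim in the opening objectives: to "confirm whether memantine is well tolerated by study participants with Down syndrome".

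Under Study Design, Procedures and Timeline, the first capsules are dispensed at the end of Visit 2. The titration is given as "5 mg/d week one, 5 mg/BID week two, 5 & 10 mg/d divided dose week three, 10mg/BID week four". The next visit is Visit 3, the "First follow-up medical visit at 8 weeks from the start of the medication", and its procedure list contains the first "Adverse Event Assessment". In Table 1 the row "Adverse Events Monitoring" is marked at Visit 3 (week 8) and Visit 5 (week 16) only.

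The safety text in the same section says that "inquiries will be made at each evaluation period as to the presence of any adverse experiences". The sample questions are general and ask about problems since the preceding visit. Laboratory tests, ECG and the SCARED anxiety questionnaire are done at baseline and week 16 only. No diary or interim call is described; the only telephone contact that the study itself makes is prescreening.

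The dose-reduction paragraph begins by saying that the dose may be lowered for mild or moderate adverse experiences once the week 8 visit has been completed.

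**The concern.** A tolerability aim needs adverse events to be asked about in a planned way while the dose is changing. Here the dose rises three times, reaches its top level and settles to steady state before anyone is scheduled to ask. What is recorded for that period then depends on two things: what a caregiver volunteers, and what is remembered at week 8.

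The events most easily lost this way are mild or short-lived behavioural ones, which may have resolved by Visit 3. Those that are remembered may carry the wrong onset date, and so cannot be tied to a dose level. At stake are the completeness of the evidence for aim 4 and, for the individual participant, how soon a problem comes to the team's attention.

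**Working it through.** The plan states no figure for this point, so there is none to reproduce. The check is one of timing. Day 0 is the first dose.

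**Inputs**
- Visit 3 (visit description and Table 1): 8 × 7 = day 56.
- Treatment length (16 weeks): 16 × 7 = 112 days.
- Dose levels by week (titration text): 5, 10, 15 and 20 mg/day in weeks 1, 2, 3 and 4 onward. That is four levels and three increases, on days 7, 14 and 21.
- Half-life (Background 1.3): "its half-life is 60–80 hours".

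**Gap in scheduled enquiry**
- Share of treatment before the first enquiry: 56 / 112 = 50%.
- Days at the top level before the first enquiry: 56 − 21 = 35.
- An event during days 0 to 28 is first asked about 28 to 56 days later, that is, after 4 to 8 weeks.

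**Steady state, five half-lives after the last increase**
- At 60 h: 5 × 60 / 24 = 12.5 days; 21 + 12.5 = day 33.5; 56 − 33.5 = 22.5 days before Visit 3.
- At 80 h: 5 × 80 / 24 = 16.7 days; 21 + 16.7 = day 37.7; 56 − 37.7 = 18.3 days before Visit 3.

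**Cross-check by accumulation**

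Assume one compartment, first-order elimination and continuous input. Let S be exposure at the end of a week as a share of the final steady state, and q = 2^(−168 / half-life in hours). Then S(week) = S(previous week) × q + (daily dose / 20) × (1 − q), where q = 0.144 at 60 h and 0.233 at 80 h.

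| Day | 60 h | 80 h |
|---|---|---|
| 7 | 21% | 19% |
| 14 | 46% | 43% |
| 21 | 71% | 68% |
| 28 | 96% | 92% |
| 35 | 99% | 98% |
| 56 | 100% | 100% |

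Exposure passes 95% of its final value on about day 27 (60 h) to day 30 (80 h). Both methods agree that the rise in exposure is over well before day 56.

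**Does another instrument fill the gap?**
- SCARED rates the past three months. From week 16, about 13 weeks back is week 3 (16 − 13 = 3), so nominally it covers the top-dose period. It does so by long recall, gives no onset dates, concerns anxiety only, and does not reach the first three weeks.
- Laboratory tests and ECG are not repeated until week 16.

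**The case against.** The strongest reply is that events before week 8 are not invisible. Inclusion criterion 12 requires a reliable caregiver with at least daily contact. At consent, caregivers are asked about their commitment to monitor and report adverse events (Vulnerable Populations). Families hold emergency telephone numbers (Risks to Research Participants). Investigators may add safety measurements at their discretion, and anyone who withdraws early is asked back for a visit with the Visit 5 procedures. The pilot's anxiety and echolalia reports came from caregivers. SCARED was added specifically to quantify anxiety. The case report form and consent form are separate appendices and may ask for onset dates or give reporting instructions.

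All of that stands as partial mitigation. None of it is a scheduled enquiry: the protocol sets no interval, prompt or form for caregiver reports, and the withdrawal visit reaches only those who leave.

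Several stronger readings are tempting and are not supported:
- **That adverse effects are most likely during titration.** The protocol gives no time course for adverse events.
- **That the pilot events were transient or arose during titration.** They are described only as infrequent and mild.
- **That the schedule biases the comparison in favour of memantine.** It is the same in both blinded arms, so the expected effect is under-counting and poor dating in each.
- **That a definite amount of power is lost for an adverse-event comparison.** The analysis plan describes no such test. The pilot anxiety rate is 2 of 18 (exact 95% interval 1.4% to 34.7%), and nothing in the documents says what fraction of events recall would keep.
- **That the safety text contradicts Table 1 over the titration period.** Both place the first on-drug enquiry at week 8.

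**Conclusion.** The gap is real and follows directly from the visit schedule. Half of treatment (56 of 112 days), with all three dose increases and 35 days at the top level, passes before the first scheduled adverse-event enquiry. Visit 3 comes about 18 to 22 days after steady state and relies on an 8-week look-back. The likely consequence is that mild or passing events during titration are under-recorded or misdated in both arms. This weakens the evidence for aim 4 and may delay recognition of problems.

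The number of events lost cannot be estimated from the documents. The steady-state dates rest on the protocol's half-life and the five-half-lives convention; the length of the gap does not depend on either.

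A related passage needs attention. The dose-reduction paragraph is worded as opening after the week 8 visit, yet the top level is reached in week 4. The sentence that follows, on not tolerating the top dose, gives no timing of its own. A reader might infer that no reduction is allowed before week 8. The text does not settle that, and it does not say how intolerance before then is identified and handled, beyond the general provision for withdrawal.

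This is a low-cost improvement worth making. It does not invalidate the design.

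**What to change.** - Add a brief telephone adverse-event enquiry to the caregiver between Visit 2 and Visit 3, made by the existing study coordinators (or their São Paulo equivalents). The sponsor should set the time or times so that they cover the titration period.
- Use the general questions already in the safety text, put identically in both arms by blinded staff. Record the onset date of each event and whether it was volunteered or prompted.
- Add the call to Table 1 and to the visit descriptions.
- Reconcile the dose-reduction paragraph with a statement of how intolerance before week 8 is identified and handled. The content of that rule is for the sponsor and investigators; none is proposed here.
- If enrolment has already begun, note who was enrolled before and after the change, so that tolerability summaries can be read accordingly.

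The cost is a protocol amendment, coordinator time (200 short calls for each scheduled time point across 200 participants) and a few more minor events to record. No clinic visit, dose or stopping rule changes.
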